8.3 Concomitant medication

A **concomitant medication** is any medication, other than metformin and liraglutide which is taken during the trial. Diabetes treatment prescribed at the end of trial should be registered in concomitant medication form in the eCRF. Medication given for a concomitant illness must be recorded in the eCRF. Insulin treatment incl. rescue medication should be registered in concomitant medication form in the eCRF. In addition there are specific forms to capture information on insulin dose in the eCRF.

Details of any concomitant medication must be recorded at trial entry (i.e. at the first visit). Any changes in concomitant medication must be recorded at each visit as they occur.

The information collected for each concomitant medication includes (at a minimum) trade name or generic name, indication, start date and stop date or continuation.

If a change is due to an AE, then this must be recorded and reported according to section [12](#). If the change influences the subject's eligibility to continue in the trial, the monitor must be informed.

8.4 Laboratory assessments

A central laboratory will be responsible for providing laboratory supplies for the analysis of blood and urine samples taken during the trial. All samples obtained during the trial will be analysed at a central laboratory or a special laboratory (PK and antibody samples). The urine pregnancy test will be performed locally during subject visits. Descriptions of assay methods, laboratory supplies and procedures for obtaining samples, handling and storage of samples and information on who will

perform the assessments, are described in a trial-specific laboratory manual provided by the central laboratory.

Laboratory samples can be drawn at another day than on the day of the actual visit as long as it is within the visit window stated in the flow chart (section [2](#)). It should be ensured that where fasting is required for the sensitivity of the analysis (Visits 1, 7, 13, 17 and 25) that subjects will attend the visit in a fasting state for blood draw.

Note: Subjects should arrive fasting for Visit 1 blood sampling. Fasting is considered a trial related activity and no trial related activities may be initiated prior to a signed assent and consent form.

Samples will be coded in order to keep subject identity anonymous.

Information on central laboratory results will be available to the investigator on an ongoing basis. All laboratory printouts must be dated and signed by the investigator on the day of evaluation. If a result is outside the normal range, the investigator must judge whether the abnormality is clinically significant and document this. If considered clinically significant the result must be reported as a concomitant illness at Visit 1 and as an AE according to section [12](#) at all other visits.

All samples will be analysed and destroyed on an ongoing basis or at the latest at the completion of the clinical trial report (CTR), unless otherwise stated.

The central laboratory equipment may provide analyses not requested in the protocol but produced automatically in connection with the requested analyses. Such data will not be transferred to the trial database, but may be reported to the investigator according to specifications in the laboratory standard operating procedures and requirements. The investigator must review all laboratory results for concomitant illnesses and AEs and report these according to this protocol.

8.5 Subject related information and assessments

8.5.1 Demography

Demography consists of:

- Date of birth (according to local regulations)
- Sex
- Race (according to local regulations)
- Ethnicity (according to local regulations)

8.5.2 Diabetes history

The following information on subject's diabetes history should be recorded:

- Date of diagnosis

- **Complications**
 - Diabetic retinopathy (incl. date of diagnosis)
 - Diabetic neuropathy (incl. date of diagnosis)
 - Diabetic nephropathy (incl. date of diagnosis)
 - Macroangiopathy including peripheral vascular disease (incl. date of diagnosis)

- **Diabetes treatment**
 - Current diabetes treatment
 - Dose of current diabetes treatment
 - Start date of current diabetes treatment

8.5.3 Smoking habits

It should be recorded at Visit 1 if the subject:

- Never smoked
- Is a previous smoker
- Is a current smoker

8.5.4 Alcohol and drug screen

A urine drug screen will be performed to test for the presence of therapeutic and drugs of abuse at Visit 1. Subjects testing positive for commonly abused substances or alcohol must not be enrolled in this trial.

8.6 Assessments for efficacy

8.6.1 Body measurements

Body measurements consist of the following parameters:

- Body weight (Visits 1, 7, 11, 12, 13, 15, 17, 18, 20, 22, 24, 25, 27 and 28)
- Height (safety endpoint) (Visits 1, 7, 13, 17, 25, 27 and 28)
- BMI (calculated at Visit 1)
- Waist circumference (Visits 1, 7, 13, 17 and 25)

Body weight

Body weight should be measured (kilogram or pound [kg or lb], one decimal) without shoes and only wearing light clothing. Preferably the same set of scales should be used throughout the trial.

Height

Height should be measured (centimetres or inches, one decimal) without shoes as two individual measurements performed by a single observer using identical technique with a Harpenden or other wall mounted stadiometer. The subject should be repositioned between the two measurements.

Waist circumference

The waist circumference is defined as the minimal abdominal circumferences located midway between the lower rib margin and the iliac crest.

Three consecutive measurements of waist circumference should be taken and recorded in the eCRF. The waist circumferences will be measured to the nearest 0.5 cm (0.2 inches) using a non-stretchable measuring tape.

The subject should be measured in a standing position with an empty bladder and wearing light clothing with accessible waist. The subject should be standing with arms down their side and feet together. The tape should touch the skin, but not compress soft tissue and twist in tape should be avoided. The subjects should be asked to breathe normally and the measurement should be taken when the subject is breathing out gently.

BMI

The BMI will be calculated by the eCRF based on the height and weight as described above. At the screening visit the investigator must verify subject's eligibility for the trial according to the BMI inclusion criteria see section [6.2](#) and Appendix A.

8.6.2 Vital signs

Vital signs will be measured at Visits 1, 5, 7, 8, 9, 11, 12, 13, 15, 17, 18, 20, 22, 24, 25 and 26. Vital signs consist of the following parameters:

- Pulse (safety endpoint)
- Systolic blood pressure, sitting
- Diastolic blood pressure, sitting

Pulse

Pulse (beats per minute) should be recorded at site visits after resting for 5 minutes in a sitting position.

Systolic and diastolic blood pressure

For measurement of systolic and diastolic blood pressure the following method should be used. Avoid caffeine, smoking and exercise at least 30 minutes prior to blood pressure measurement. The measurement should be taken in a sitting position, with legs uncrossed, the back and arm supported. Subjects should be sitting for at least 5 minutes before the first measurement is taken. The subject

should not talk during the measurement. The site should measure blood pressure using their usual method, the method should be consistent throughout the trial using the same devices. For blood pressure at screening visit (Visit 1) three measurements need to be performed and all three values should be entered into the eCRF. The mean value will be calculated by the eCRF system and must be in accordance with exclusion criterion 21 (see section [6.3](#) and Appendix B). It is recommended to use the same arm used at Visit 1 for measurements of pulse and blood pressure at subsequent visits.

If investigator suspects white coat hypertension at the screening visit one re-assessment of the systolic and diastolic blood pressure (using the same procedure as described above) is allowed as described in exclusion criterion 21.

In case of an “abnormal, clinically significant” finding, the investigator must comment in the medical records and, if it occurs at Visit 1, record this on the concomitant illness form. Any clinically significant worsening from baseline during the trial must be reported as an AE.

8.6.3 Blood samples

Blood samples will be drawn at site at the specified time-points (section [2](#)) and analysed at the central laboratory to determine levels of the following efficacy laboratory parameters:

- Glucose metabolism
 - HbA_{1c}
 - FPG
 - Fasting C-peptide
 - Fasting insulin
 - Fasting pro-insulin
 - Fasting glucagon

- Lipids
 - Cholesterol
 - LDL cholesterol
 - HDL cholesterol
 - VLDL cholesterol
 - Triglycerides
 - Free fatty acids

8.6.4 Self-measured plasma glucose

At Visit 2, subjects should be supplied with a glucose meter and oral and written instruction on use of the device including regular calibration according to the manufacturer's instructions. Sites should as necessary, repeat the instruction of use at visits to the clinic. Subjects already treated with metformin 2000 mg/day at a stable dose for at least 56 days prior to screening may have their BG meter for Visit 7 provided at Visit 1.

The glucose meters use test strips calibrated to plasma values. Therefore, all glucose measurements performed with drawn capillary blood are automatically calibrated to plasma equivalent glucose values, which will be shown on the display and are values to be used.

Subjects should be instructed in how to record the results of the SMPG values (including date) in the provided diaries and should only record the SMPG values based on glucose meter measurements.

Self-measured plasma glucose

Subjects will be asked to perform fasting SMPG measurements on the 3 consecutive days preceding Visit 7. The average of these 3 measurements will be used to evaluate subject's eligibility according to randomisation criterion no. 1 (see section 6.4).

After randomisation, subjects will be asked to perform fasting SMPG measurements on the 3 consecutive days preceding Visits 8, 9 and 10. Subjects treated with basal insulin will be asked to perform fasting SMPG measurements on the 3 consecutive days preceding Visits 10A, 10B, 11A and 11B for adjustment of insulin dose. For all other subjects fasting SMPG measurements should be performed 3 times a week (on a weekly basis) between Visits 10 and 11. The measurements should be captured in the subjects' diary. These measurements are used to evaluate the safety of the subject during their first weeks of treatment with liraglutide. In addition the first two to three weeks' measurements are used for dose escalation of liraglutide.

In addition all subjects are encouraged to measure their FPG on a regular basis as agreed with the investigator. Also subjects should measure their plasma glucose at least every time the subject has symptoms of hypoglycaemia or hyperglycaemia. Hypoglycaemic episodes should be recorded in the diary (see section [8.1](#)). The investigator may ask the subject to perform additional SMPGs if needed for any safety reason.

The subject should be instructed to contact the Investigator if:

- self-measured FPG falls below 3.9 mmol/L (70 mg/dL),
- or if:
- During the first 14 weeks after randomisation: FPG increases above 12.2 mmol/L (220 mg/dL) on three consecutive days, or if:

- After Week 14 (Visit 13): FPG increases above 10.3 mmol/L (185 mg/dL) on three consecutive days

The outcome of the contact will be recorded on an Unscheduled Visit Form.

7-point self-measured plasma glucose profile

Subjects will be instructed to perform a 7-point SMPG profile preferably within one week prior to Visits 7, 13, 17 and 25 on days where the subject do not anticipate unusual strenuous exercise.

The plasma glucose levels should be measured and recorded in the diary (including date, actual, clock time and plasma glucose value) at the following time points, always starting with measurement just before breakfast.

Time-points for 7-point profile:

- Before breakfast
- 90 min after the start of breakfast
- Before lunch
- 90 min after the start of lunch
- Before dinner
- 90 min after the start of dinner
- At bedtime

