• HbA _{1c}	X						X							X				X							X				
• Fasting plasma glucose	X						X							X				X					X			X			
• Fasting insulin							X							X				X								X			
• Fasting pro-insulin							X							X				X								X			

10. At Visits 1, 7, 13, 17 and 25 a blood pregnancy test will be performed in females of childbearing potential. In addition at Visit 7, prior to randomisation, a urine-stick pregnancy test will be performed. During the rest of the trial a urine-stick pregnancy test will be performed if a menstrual period is missed.
Austria: Urine-stick pregnancy test will be performed at all visits to the clinic.
11. PK sampling will be performed at Visit 11 only.
12. Blood sampling for HbA_{1c} and dispensing of urine container will be performed at Visit 12 only.
13. First day of the most recent menstrual period should be captured for females of childbearing potential in the diary prior to Visits 7, 13, 17 and 25.
14. Fasting SMPG measurements should be performed and captured in the diary on 3 consecutive days prior to Visits 7, 8, 9 and 10. Subjects treated with basal insulin at screening will be asked to perform fasting SMPG measurements on the 3 consecutive days preceding Visits 10A, 10B, 11A and 11B. For all other subjects fasting SMPG measurements should be performed 3 times a week (on a weekly basis) between Visits 10 and 11.
15. Subjects already treated with metformin 2000 mg/day for at least 56 days prior to screening may have their BG meter, urine collection container for Visit 7 provided at Visit 1 and advance directly to Visit 7. Subjects who are treated with basal insulin should in addition to the stable dose of metformin have a stable dose of basal insulin for at least 56 days to advance directly to visit 7.
16. In case an extra week for titrating to 2000 mg or maximum tolerated dose of metformin is needed, the titration period can be extended with an additional week, from 3 to 4 weeks. An unscheduled visit between Visits 4 and 5 may be performed to ensure compliance and the safety of the subject before the last dose step at the discretion of the investigator. All subjects who undergo metformin titration including those who require a fourth week to reach a dose of metformin of 2000mg or a maximum tolerated dose, need to undergo the full 8 weeks maintenance period with 2000 mg or maximum tolerated dose of metformin before randomisation.

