17. At Visits 7, 13, 17, 25, 27 and 28 the assessments may be performed in the two weeks prior to the visits. Once the subject reaches the Tanner stage V, the Tanner staging assessment no longer requires to be performed.
18. A repeat bone age assessment will not be performed for subjects in whom the bone age assessment at the previous assessments indicates that the epiphyses are fused.
19. Visits 27 and 28 are only applicable for subjects treated with liraglutide for more than 3 months.
20. Prior to blood sampling for liraglutide antibodies subjects must attend without food or drink intake except for water and prescribed medication for at least 2 hours.
21. Visits 10A, 10B, 11A and 11B are only applicable to subjects treated with basal insulin.
22. Basal insulin titration only applicable at Visit 11.
23. Only applicable to subjects treated with basal insulin.
- Explanations:** Rand = randomisation; S = site visit; TC= telephone contact

3 Background information and rationale for the trial

In this document, the term investigator refers to the individual responsible for the overall conduct of the clinical trial at a trial site.

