5.3.3 Basal insulin

Subjects may enter the trial on a stable dose of basal insulin. A stable dose of basal insulin (intermediate acting human insulin, intermediate acting insulin analogue or long acting insulin analogue) is defined as basal insulin adjustments up to 15% at the investigator's discretion. Subjects treated with basal insulin must initiate treatment with metformin as described in section 5.3.).

The pre-trial basal insulin regimen will be considered background medication and will not be provided by Novo Nordisk.

Subjects treated with basal insulin at screening should reduce their basal insulin dose by 20% at randomisation.

Subjects on a stable dose of metformin ≥ 2000 mg as per section 5.3.1 can advance directly to maintenance period or randomisation depending on the time on stable insulin:

- Subjects with a stable dose of basal insulin for at least 30 days but less than 56 days at screening (visit 1) may proceed directly to the 8 week maintenance period (Visit 5)
- Subjects on a stable dose of basal insulin for 56 days or more at screening (Visit 1) may advance directly to randomisation (Visit 7) when eligibility according to the inclusion and exclusion criteria has been confirmed.

After the MTD dose of liraglutide/liraglutide placebo is reached, the dose of basal insulin can be up-titrated to no higher than the screening dose level. This up-titration will be based on the average of three pre-visit fasting SMPG values before visits between weeks 4 and 8 (Visits 10A -11B). Up-titration is only allowed between Visits 10A and 11B. Up-titration of basal insulin dose is to be performed at the discretion of the investigator in accordance with the algorithm described in Table 5-1.

Table 5–1 Algorithm for up-titration of basal insulin dose

Average fasting SMPG	Increase in basal insulin dose
>10 mmol/L (>180 mg/dL)	+6 units
7.8 to 10 mmol/L (141–180 mg/dL)	+4 units
6.7 to <7.8 mmol/L (121–140 mg/dL)	+2 units
5.6 to <6.7 mmol/L (100–120 mg/dL)	+1 units

SMPG=self-measured plasma glucose

(adapted from the Texas Diabetes Council 2013²¹)

Basal insulin should be down-titrated for unexplained hypoglycaemia ≤ 3.9 mmol/L (≤ 70 mg/dL) at any time during the trial at the discretion of the investigator in accordance with Table 5-2

Table 5–2 Algorithm for down-titration of basal insulin dose

PG	Reduction of basal insulin dose

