8.1.5 Visits

Procedures for the scheduled site visits and phone contacts are described in the following section and in the flow chart (please refer to section [2](#)). In order to secure consistency in data over time it is encouraged that assessments are performed consistently (e.g. using the same type of equipment and trial site staffs with alike qualifications) during the trial.

For visit numbers, timing of site visits, phone contacts and visit windows during the trial period, please refer to the flow chart (section [2](#)). It is the responsibility of the investigator to ensure that all site visits and phone contacts occur according to the flowchart. A phone contact may be converted to a site visit, if needed.

There will be one follow-up visit (Visit 26) for all subjects. Subjects treated with liraglutide for more than 3 months should in addition attend a 1 and 2 year follow-up visit (Visits 27 and 28). There will be no diaries attached to these visits and hence reporting of AEs and SAEs will be by the subject's and subject's LAR's memory.

Visits attended fasting

Subjects must attend the clinic in a fasting state for Visits 1, 7, 13, 17, 22 and 25 blood sampling. Fasting is defined as at least eight hours without food or drink intake except for water and prescribed medication other than diabetes medication.

In addition subjects must be without food or drink intake except for water and prescribed medication for at least 2 hours before Visit 26 blood sampling.

Should a subject attend a fasting blood sampling in a non-fasting state blood sampling must be re-scheduled, preferably within the visit window.

Unscheduled and missed visits

If a subject attends the clinic for an unscheduled visit, the unscheduled visit form must be completed unless the subject attends the clinic to obtain additional IMP, NIMP, auxiliary supplies or to perform a re-test of a blood sample. If the subject needs additional IMP and/or NIMP an additional dispensing call should be made in the IV/WRS.

Should a visit be missed, every effort should be made to re-schedule the visit within the allowed visit window. If this is not possible the visit should be re-scheduled at the earliest possible date.

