Rescue and withdrawal criteria are defined to ensure that subjects are considered for rescue treatment or withdrawal if the level of glycaemic control exceeds acceptable limits during both the blinded and un-blinded periods.

Subjects treated with basal insulin at screening should reduce their insulin dose by 20% at randomisation to limit the potential risk of hypoglycaemic episodes induced by the combined therapy of basal insulin and liraglutide. Once reaching the maximum dose of liraglutide/liraglutide placebo basal insulin treatment can be titrated up to no higher than pre-trial dose levels to ensure that treatment in the placebo arm is comparable to the pre-randomisation treatment.

Throughout the trial, subjects will be in regular contact (by telephone or visits) with the investigator or designated persons. Blood sampling and contacts with the clinic are considered an inconvenience for the children and adolescents participating in the trial. On the other hand, the intensified treatment may help to improve glycaemic control.

During the trial (incl. 2 year's follow-up period) up to 4 x-rays of left hand and wrist will be performed. When performing the x-rays the subject will be exposed to x-ray radiation. The amount of x-ray radiation when performing the x-rays is comparable to the amount of background radiation received from the surroundings in the United States during a period of approximately 3 days. This means that the risk of cancer will increase with 0.000125% for the x-rays performed.

Currently liraglutide does not have regulatory approval for treatment of paediatric subjects. However liraglutide has been approved by the authorities for use in adults in more than 60 countries including the US, China and the EU.

The trial product may be associated with AEs, but relevant precautions have been implemented in the design and planned conduct of the trial in order to minimise the risks and inconveniences of trial participation. These precautions include providing thorough information regarding the correct administration of the trial drugs and gradual dose adjustment. Furthermore, subjects and subjects'

LAR are fully informed about possible AEs and inconveniences and will be instructed to contact the investigator in case of any concerns regarding the trial participation.

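### Visit 11 (week 6) is a basal insulin up-titration visit, but insulin-treated subjects have no fasting readings scheduled before it

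*Protocol*

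**What the plan says.** Subjects on basal insulin at screening cut their dose by 20% at randomisation (protocol section 5.3.3). Once the maximum tolerated dose of trial product is reached, "the dose of basal insulin can be up-titrated to no higher than the screening dose level". Each increase is "based on the average of three pre-visit fasting SMPG values before visits between weeks 4 and 8", and section 5.3.3 confines increases to the span from Visit 10A to Visit 11B. Section 18 gives the purpose: insulin may be "titrated up to no higher than pre-trial dose levels to ensure that treatment in the placebo arm is comparable to the pre-randomisation treatment".

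The flow chart (section 2) places Visits 10A and 10B at weeks 4 and 5, Visit 11 at week 6, and Visits 11A and 11B at weeks 7 and 8. Visits 11 and 12 share one column, and note 22 says of it: "Basal insulin titration only applicable at Visit 11".

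The readings that feed these decisions are set out in two places. Section 8.6.4 requires "fasting SMPG measurements on the 3 consecutive days preceding Visits 10A, 10B, 11A and 11B for adjustment of insulin dose". Note 14 says that subjects on basal insulin at screening will be "asked to perform fasting SMPG measurements on the 3 consecutive days preceding Visits 10A, 10B, 11A and 11B". Section 8.6.4 then adds: "For all other subjects fasting SMPG measurements should be performed 3 times a week (on a weekly basis) between Visits 10 and 11".

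**The concern.** The titration rule and the schedule that supplies its data do not match. A site that follows the reading schedule exactly reaches Visit 11 without the three values that section 5.3.3 requires. It must then skip the step, use old readings, or arrange extra ones on its own initiative.

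Two things are at stake. The first is the section 18 aim of bringing placebo subjects back to their treatment before randomisation: some subjects would regain their dose later or not fully. The second is monitoring. Section 8.6.4 says that the early fasting readings also serve to evaluate safety. Straight after a possible insulin increase at Visit 10B, insulin-treated subjects have no scheduled fasting readings, while subjects not on insulin have three a week up to Visit 11.

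**Working it through.** The plan states no figure to reproduce here. The check matches titration visits to scheduled readings and then works out what a missed step can cost.

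**Coverage** (weeks from the flow chart; readings from section 8.6.4 and note 14)

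| Visit | Week | Nominal day | Titration visit | Three-day readings scheduled |
|---|---|---|---|---|
| 10A | 4 | 28 | yes | yes |
| 10B | 5 | 35 | yes | yes |
| 11 | 6 | 42 | yes | no |
| 11A | 7 | 49 | yes | yes |
| 11B | 8 | 56 | yes | yes |

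Four of five decisions have scheduled input. Visit 11 does not.

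**Can neighbouring readings fill in?** The windows are ±2 days for 10B and 11A and ±3 days for Visit 11.

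- Readings before 10B fall nominally on days 32 to 34, so the newest is 42 − 34 = 8 days old at Visit 11. They also precede any dose change made at 10B.
- In the most favourable case 10B is on day 37 (readings on days 34 to 36) and Visit 11 on day 39. The readings still precede the 10B decision.
- The earliest 11A is day 47, with readings on days 44 to 46. The latest Visit 11 is day 45, so the full set for 11A cannot be complete by then.

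**Length of the gap.** From 10B to the first reading for 11A:

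- nominal: (49 − 3) − 35 = 46 − 35 = 11 days
- shortest: (47 − 3) − 37 = 44 − 37 = 7 days
- longest: (51 − 3) − 33 = 48 − 33 = 15 days

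**Other sources.** The laboratory offers no substitute: "Subjects must attend the clinic in a fasting state for Visits 1, 7, 13, 17, 22 and 25 blood sampling", and Visit 11 is not in that list.

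**Dose effect of skipping Visit 11.** Let D be the screening dose and k the step from Table 5-1 (+6, +4, +2 or +1 U). Assume that the step is constant. The amount to restore is 0.2D, and n steps suffice if nk ≥ 0.2D, that is D ≤ 5nk.

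| Steps | Condition | k = 6 | k = 4 | k = 2 | k = 1 |
|---|---|---|---|---|---|
| 2 (weeks 4, 5) | D ≤ 10k | 60 U | 40 U | 20 U | 10 U |
| 4 (Visit 11 skipped) | D ≤ 20k | 120 U | 80 U | 40 U | 20 U |
| 5 (all visits) | D ≤ 25k | 150 U | 100 U | 50 U | 25 U |

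- D ≤ 10k: no effect, because the dose is already restored by week 5.
- 10k < D ≤ 20k: full restoration comes one week later (week 7 instead of 6, or week 8 instead of 7).
- D > 20k: the shortfall at week 8 is min(0.2D, 5k) − 4k, which is at most k. As a share of D it peaks at D = 25k, where it is k/25k = 4%.

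**The case against.** The strongest reply is that this is a slip in a list with hardly any consequence. Increases are at the investigator's discretion, so a skipped step is never a deviation. Two further titration visits with readings follow. Section 6.5 starts rescue for insulin-treated subjects only after week 8, so a delay before then cannot itself trigger rescue. Down-titration for hypoglycaemia is allowed at any time and does not use these averages. All of this stands, and it is why the effect is small. One qualification is that up-titration ends at Visit 11B, so section 5.3.3 offers no later step to make good a remaining shortfall.

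It can also be said that sites can obtain readings anyway. Section 8.6.4 encourages regular self-measurement of fasting glucose and lets the investigator request extra readings for safety reasons. Section 5.3.3 does not demand consecutive days. That narrows the gap in practice, but neither provision schedules three readings before Visit 11, so the outcome depends on site habit.

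The flow-chart rows for self-measured glucose and insulin titration are not in the text available to us, and they might mark Visit 11. The explicit visit lists in section 8.6.4 and note 14 would still omit it, and would then contradict the chart as well.

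Finally, the dose model assumes a constant step, while Table 5-1 sets each step from current glucose. This is fair: a missed increase may lead to a larger one at 11A, and with unequal steps 4% is not a strict bound.

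**Conclusion.** The concern holds. The titration rule covers Visit 11 and the reading schedule leaves it out, in both places where that schedule is stated. One of five titration decisions lacks scheduled input, with about 11 days (7 to 15) between the days with scheduled readings on either side.

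The consequence is minor and confined to subjects on basal insulin. On the constant-step assumption, the worst case is one step lost at week 8, at most 4% of the screening dose. The documents give neither the screening insulin doses nor the share of subjects on basal insulin, so the number affected is unknown. Sample size, power and the primary analysis are unchanged. The correction is still worth making: the text contradicts itself on insulin dosing in children, and it is cheap to put right.

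That Visit 11 is a titration visit rests on section 5.3.3 and note 22, which agree.

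**What to change.** In section 8.6.4 and in flow-chart note 14, change the visit list for insulin-treated subjects to Visits 10A, 10B, 11, 11A and 11B. All five titration visits in section 5.3.3 then have their three readings, and the gap after Visit 10B closes. If the flow-chart row for self-measured glucose does not mark Visit 11 for these subjects, correct it at the same time.

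The cost is one visit number in two places, one diary line, and at most three extra finger-stick readings per insulin-treated subject.
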